2.5 Analysis of the primary and secondary endpoint

2.5.1 Primary endpoint

The definition and rationale for the estimand for the primary endpoint are given in [Table 2-2](#). Novartis proposes the most informative estimand to be one that considers the maintenance treatment effect that could be expected in clinical practice. The statistical strategy to handle each intercurrent event is described in more detail in [Section 2.5.4](#).

Table 2-2 Summary of estimand for the primary endpoint

Population
Male or female patients aged 12 years and older with asthma, who are uncontrolled with SoC therapy and receive at least one dose of study treatment. For this study, SOC is defined as ICS or ICS with a second controller medication (LABA or LTRA)

Variables
Change from baseline in pre-dose FEV ₁ at the end of 12 weeks of treatment

Intercurrent event	Description	Strategy to handle event	Justification
Asthma medications with an effect on FEV ₁ are taken within washout periods prior to spirometry assessment.	Allowed asthma medications (including SABA and SoC treatment) are taken within washout periods prior to spirometry assessment. Wash-out periods for allowed asthma medications prior to spirometry assessments are defined in Protocol Table 5-2.	A hypothetical strategy will be used for the days on which these medications are taken within the washout periods.	Asthma medications that taken within washout periods may have a transient impact on FEV ₁ but interest is primarily in the effect of longer-term maintenance therapy.
Discontinuation of fevipirant for any reason	Discontinuation of fevipirant for any reason regardless of relation to fevipirant	A treatment policy strategy will be used. All efforts will be made to retain patients in the trial and adhere to the schedule even after discontinuation of fevipirant/placebo. Where those efforts are not successful, the missing observations will be imputed as described in Section 2.5.4	These patients may discontinue therapy in clinical practice. Any fevipirant treatment effect would cease almost instantly after discontinuation of fevipirant, and only SoC effect is expected.
Discontinuation of placebo for any reason	Discontinuation of placebo for any reason	A treatment policy strategy will be used. All efforts will be made to retain patients in the trial and adhere to the schedule even after discontinuation of fevipirant/placebo. Where those efforts are not successful, the missing observations will be imputed as described in Section 2.5.4	In clinical practice, patients receive SoC without additional treatment and the approach for placebo reflects this.

Summary measures

mean difference in change from baseline in pre-dose FEV₁ (L) at week 12 between treatment groups

2.5.2 Secondary endpoints

The secondary endpoints are daytime asthma symptoms, total daily SABA use and AQLQ+12. Their definition and analysis is described in [Section 2.6](#).

2.5.3 Statistical hypothesis, model, and method of analysis**2.5.3.1 Primary endpoint**

The primary objective of the study is to evaluate superiority of QAW039 150 mg once daily over placebo (with SoC asthma therapy as the background therapy) by testing the following null hypothesis (H₀) versus the alternative hypothesis (H_a):

H₀: There is no difference in the change from baseline in pre-dose FEV₁ (L) at week 12 post-baseline for the patients treated with QAW039 150 mg once daily compared with placebo ($\mu_1 - \mu_2 = 0$)

H_a: There is a difference in the change from baseline in pre-dose FEV₁ (L) at week 12 post-baseline for the patients treated with QAW039 150 mg once daily compared with placebo ($\mu_1 - \mu_2 \neq 0$).

where;

μ_1 = Mean change from baseline in pre-dose FEV₁ (L) at week 12 of QAW039 150 mg once daily treatment;

μ_2 = Mean change from baseline in pre-dose FEV₁ (L) at week 12 of Placebo treatment;

The primary efficacy variable will be analyzed on the FAS using an analysis of covariance (ANCOVA) model with factors for treatment group, randomization strata [age group (<18 vs. ≥18 years), use or non-use of a second asthma controller medication at study entry, and region], as well as the baseline daytime asthma symptom score, baseline total daily SABA use and baseline pre-dose FEV₁ as continuous linear covariates. The variables contributing to the randomization strata (i.e. age group (<18 vs. ≥18 years), use or non-use of a second asthma controller medication at study entry, and region) are included separately in the model.

The least squares mean (“adjusted mean”) change from baseline for each treatment group, the difference in the least squares (LS) mean changes between the two treatment groups (QAW039 150 mg – placebo), and the two-sided 95% confidence interval along with the p-value for the difference will be obtained and combined from the primary analysis model through the multiple imputation approach described in [Section 2.5.4](#).

The superiority of QAW039 150 mg once daily to placebo as add on to SoC asthma therapy is established if the two-sided p-value is less than 0.05 and the 95% confidence intervals lie entirely to the right of 0 L.

Summary statistics for the primary endpoint

Summaries of observed absolute values and change from baseline in pre-dose FEV₁ (L) by treatment group and visit will be presented.

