### **Treatment period**

During this period, oral QAW039 150 mg or matching placebo (1:1) will be administered once daily for 12 weeks added to SoC asthma therapy (as defined in inclusion criterion 4), with the last dose given at Week 12 and final assessment for the treatment period at Week 12. The 12-week treatment duration is considered sufficient to demonstrate an effect of QAW039 on the primary endpoint, pre-dose FEV1, in this Phase 3 study since QAW039 has previously demonstrated significant effects on pre-dose FEV1 in 12-week Phase 2 studies.

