Pregnancy test—urine dipstick test in clinic (women of child bearing potential)			X			X	X	X	X	X	Pregnancy testing will begin at the visit a patient is first identified as being of child bearing potential. A positive urine pregnancy test requires immediate interruption of study drug until serum β-hCG is performed and found to be

Period	Screen	Placebo Run-in		Treatment						Follow-up	Notes
Visit Number (Site visits)	1	101	199	201	202	203	204	TD	299	301	Follow-up Visit 301 is only applicable for patients not participating in the safety study.
Treatment Week	-3	-1	0	0	2	4	8	TD	12	16	Visit 199 and Visit 201 occur on the same day.
Treatment Day	-21	-7	1	1	14	28	56		84	112	
											negative. If positive, the patient must be discontinued from study drug.
Urinalysis and urine chemistry (central laboratory)	X			X				X	X		
Blood sample for hematology and chemistry (central laboratory)	X			X				X	X		No fasting requirement prior to blood sampling.
Blood sample for RAST/ImmunoCAP test (central laboratory)	X										
Review Visit 1 laboratory results		S									If results for chemistry, hematology, HbA1c, RAST/ImmunoCAP, urine chemistry and urinalysis are missing, obtain a repeat for the missing result.
Parasitic screening	S										Only if required by health authority and/or ethics committee/ institutional review board. Sites should use local laboratories.
Spirometry (centralized)	X							X			
1 st Pre-dose Spirometry (centralized) approximately - 45 min. pre-dose		X		X	X	X	X		X		To be performed approximately 45 min. prior to in-clinic witnessed study drug administration.
2 nd pre-dose Spirometry (centralized) approximately -15 min. pre-dose		X ε		X	X	X	X		X		To be performed approximately 15 min. prior to in-clinic witnessed study drug administration.

Period	Screen	Placebo Run-in		Treatment						Follow-up	Notes
Visit Number (Site visits)	1	101	199	201	202	203	204	TD	299	301	Follow-up Visit 301 is only applicable for patients not participating in the safety study.
Treatment Week	-3	-1	0	0	2	4	8	TD	12	16	Visit 199 and Visit 201 occur on the same day.
Treatment Day	-21	-7	1	1	14	28	56		84	112	
											£To be performed prior to reversibility test.

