### Statistical model for primary variable

The primary efficacy variable will be analyzed on FAS using an analysis of covariance (ANCOVA) model with factors for treatment group, age group (<18 vs.  $\geq 18$  years), use or non-use of a second asthma controller medication at study entry, and region, as well as the baseline daytime asthma symptom score, baseline total daily SABA use and baseline pre-dose FEV1 as continuous linear covariates.

The least squares mean (“adjusted mean”) change from baseline for each treatment group, the difference in the least squares mean changes between the two treatment groups (QAW039 150mg – placebo), and the two-sided adjusted 95% confidence interval along with the p-value for the difference will be obtained and combined from the primary analysis model through the multiple imputation approach described in Section 9.4.3. The superiority of QAW039 150 mg once daily to placebo as add on to SoC asthma therapy is established if the two-sided p-value is less than 0.05 and the 95% confidence intervals lie entirely to the right of 0 L.

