2.1.1.1 Baseline definition

Data from unplanned visits prior to screening are not included in analysis. In general, baseline is defined as the last assessment taken prior to the first dose of study drug at Day 1 (Visit 201).

Checks will be performed to ensure the assessments were taken prior to the first dose of study drug on Day 1 (Visit 201). If the assessment is missing or not confirmed to be pre-dose, then the last available non-missing assessment will be used as baseline. Missing baseline pre-dose FEV1, daytime asthma symptoms, total daily SABA use and AQLQ+12 will be assumed to be missing at random as assessments are performed prior to any knowledge of treatment allocation and will be imputed using the mean value of all randomized patients.

Table 2-1 Baseline definition of analysis parameters

Parameter	Baseline assessment	Detail
ACQ-5, AQLQ [REDACTED]	Last assessment prior to the first dose of study drug on Day 1	If the Day 1 assessment is missing the last available assessment (scheduled or unscheduled) taken prior to the first dose of study drug will be used.

Lung function (FEV ₁)	Average of the two FEV ₁ assessments taken at 45 minutes and 15 minutes prior to the first dose of study drug on Day 1	Checks will be performed to ensure both values were taken prior to the first dose of study drug. If one of the 45 and 15 min values is missing (or is not confirmed to be pre-dose) then the remaining non-missing value will be taken as the baseline. If both assessments are missing (or are not confirmed to be pre-dose) then the last available FEV ₁ measurement (scheduled or unscheduled) prior to Day 1 will be used for baseline.
eDiary data (Daytime asthma symptoms)	Average of the mean daytime asthma symptom score from Visit 101 to Day 1	The baseline score will be calculated as long as there are at least 4 days with non-missing eDiary data. Noted that the morning assessment for Day 1 counts towards the baseline.
eDiary data (Total daily use of SABA)	Average of total daily SABA use from Visit 101 to Day 1	The baseline score will be calculated as long as at least 4 days with non-missing eDiary data. Noted that the morning assessment for Day 1 counts towards the baseline while the evening assessment for Day 1 counts as the treatment period.

Laboratory data (hematology, clinical chemistry, urine analysis)	Last available assessment (scheduled or unscheduled) prior to dosing on Day 1	

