2.12 Interim analysis

No interim analysis for efficacy is planned in this study. An independent, external DMC has been set up to review safety data (including specific safety summaries for adolescent participants) for this trial. No statistical adjustment will be made to the final analysis.

3 Sample size calculation

The primary objective is to demonstrate that QAW039 150 mg is superior to placebo in pre-dose FEV1 following 12 weeks of post-baseline treatment. A difference of 112 mL in pre-dose FEV1 during treatment was assumed, which is similar to the model-averaged effect seen in

study QAW039A2206. The standard deviation (SD) of 380 mL and between-visit correlation for pre-dose FEV1 was based on study QAW039A2206 in a similar population. A treatment discontinuation rate of 15% was assumed based on QAW039A2206 and it was assumed that half of the patients discontinuing study treatment would have week 12 FEV1 values. Simulations were used to determine the sample size due to the complex J2R missing data imputation approach for the primary analysis.

Under the outlined assumptions, a sample size of 650 patients (325 per arm) would be needed to have 90% power to observe a statistically significant difference between QAW039 and placebo at the two-sided 5% significance level in the primary analysis as shown in [Table 3-1](#). The table also shows the sensitivity of the power to deviations from the assumptions.

Table 3-1 Result of power simulations for the primary variable

Treatment effect (mL)	Discontinuation rate	Sample size	Power
112	15%	650	90.3
112	20%	650	85.9
100	15%	650	80.9

Based on 10,000 simulated trials per scenario and 250 multiple imputations for each trial. Simulations were conducted using SAS/STAT® 13.1 software, Version 9.4 of the SAS System for Linux.

Power for the secondary objectives

If statistical significance is achieved in the primary test, the tests for the secondary variables will be performed. The local significance level for each secondary null hypothesis will be determined based on the closed testing procedure shown in [Figure 2](#).

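### Adding the Visit 101 pre-dose FEV1 as a second baseline covariate in the primary ANCOVA would cost almost nothing and could add anywhere from zero to about six points of power

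*SAP*

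**What the plan says.** SAP 2.5.3.1 specifies an ANCOVA with factors for treatment, age group, second controller and region, plus "baseline daytime asthma symptom score, baseline total daily SABA use and baseline pre-dose FEV₁ as continuous linear covariates". Protocol 9.4.2 gives the same continuous covariates: "baseline daytime asthma symptom score, baseline total daily SABA use and baseline pre-dose FEV1 as continuous linear covariates".

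SAP Table 2-1 defines baseline FEV1 as the mean of the two Day 1 readings. An earlier value enters only if both are unusable: "then the last available FEV ₁ measurement (scheduled or unscheduled) prior to Day 1 will be used for baseline".

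Protocol Table 6-1 marks both pre-dose spirometry tests at Visit 101 (Day -7) as well as at Visit 201. The note to the first reads "To be performed approximately 45 min. prior to in-clinic witnessed study drug administration"; the second is placed before the reversibility test. Inclusion criterion 5 needs an FEV1 at Visit 101 after bronchodilators have been withheld, and protocol 6.4.1 provides central over-read.

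SAP 2.5.4 requires the imputation model to carry the same covariates as the primary model. The example call in SAP 6.6.1 lists baseline FEV1, symptom score and SABA use.

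**The concern.** The run-in is there to collect baseline data (protocol 3.2). SAP Table 2-1 averages baseline symptoms and baseline SABA use over the days from Visit 101 to Day 1. FEV1, the primary variable, is the only continuous covariate that rests on a single morning.

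If a patient's FEV1 varies from day to day, one morning is a noisy measure of that patient's level, and a second morning carries further prognostic information. Leaving it out can make the standard error of the primary treatment difference larger than the collected data require. The primary test is also the gatekeeper for all three secondary hypotheses (SAP 2.5.6), so any margin gained there serves the whole hierarchy.

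**Working it through.** **Inputs (SAP Section 3; protocol 3.2 for 1:1 allocation).** 325 per arm, two-sided 5%, effect 112 mL on treatment, SD 380 mL, 15% discontinuation, half of the discontinuers with a Week 12 value, simulated power 90.3%. A between-visit correlation was used, but its value is not given. Nor do the documents say whether 380 mL is the SD of the change or the residual SD.

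**Step 1. Reproduce the plan's figure.** Treat every discontinuer as losing the effect, so the effect is δ(1 − d), and take 380 mL as the residual SD:

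power = Φ( δ(1 − d) / (380·√(2/325)) − 1.96 ), with 380·√(2/325) = 29.8 mL.

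| Effect, discontinuation | Diluted effect | Computed | Stated |
|---|---|---|---|
| 112 mL, 15% | 95.2 mL | 89.1% | 90.3% |
| 112 mL, 20% | 89.6 mL | 85.2% | 85.9% |
| 100 mL, 15% | 85.0 mL | 81.4% | 80.9% |

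All three agree within 2 points.

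**Step 2. Variance factor.** Write a for the correlation of Day 1 with Week 12, b for Visit 101 with Week 12, and c for Visit 101 with Day 1. With one baseline the residual variance is proportional to 1 − a². With two it is 1 − R², where R² = (a² + b² − 2abc)/(1 − c²). The factor is (1 − R²)/(1 − a²). With equal correlation r it becomes (1 + 2r)/(1 + r)².

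**Step 3. Power.** The noncentrality behind 90.3% is 1.299 + 1.960 = 3.259. New power = Φ(3.259/√factor − 1.96). All correlations below are assumptions.

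| a / b / c | Factor | Power |
|---|---|---|
| pure decay with time (b = ac) | 1.00 | 90.3% |
| 0.80 / 0.75 / 0.92 | 0.996 | 90.4% |
| 0.80 / 0.78 / 0.90 | 0.95 | 91.7% |
| 0.80 / 0.78 / 0.88 | 0.93 | 92.2% |
| equal, 0.6 | 0.86 | 94.0% |
| equal, 0.8 | 0.80 | 95.3% |
| equal, 0.9 | 0.78 | 95.9% |

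From the 89.1% base of Step 1, equal correlations of 0.8 and 0.9 give 94.6% and 95.2%. If 380 mL is instead the SD of the raw change, the same two cases go from 92.0% to 96.4% and from 90.6% to 96.1%.

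**Step 4. Check under jump-to-reference imputation.** A simulation with 1,000 trials and 25 imputations per scenario (Monte Carlo error about 1 point) compared the models without and with Visit 101 FEV1:

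| a / b / c | Mean SE (mL) | Power |
|---|---|---|
| equal, 0.8 | 31.0 → 27.9 | 88.4% → 93.3% |
| equal, 0.9 | 31.1 → 27.4 | 89.4% → 94.8% |
| 0.85 / 0.84 / 0.90 | 31.1 → 29.4 | 87.3% → 90.6% |
| 0.80 / 0.79 / 0.95 | 31.0 → 30.7 | 88.5% → 89.3% |
| pure decay | 31.04 → 31.07 | no gain beyond simulation error |

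**Step 5. Downside.** One degree of freedom out of about 640 costs less than 0.1 power point.

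**Step 6. Is no gain the expected case?** Pure decay leaves no visit-specific noise. If the true level decays as φ per week and each visit's reading has reliability L, then a = Lφ¹², b = Lφ¹³ and c = Lφ. The partial covariance is b − ac = L(1 − L)φ¹³, which is positive whenever L < 1. Some noise is expected: Appendix 5 of the protocol tolerates 0.150 L between the two best efforts. That is a within-session limit, however, and does not measure day-to-day variation.

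**The case against.** The strongest reply is that nothing in the plan is wrong. Protocol and SAP name the same covariates, the model is pre-specified and valid, and it reaches its 90% target. Which prognostic covariates to add is partly a matter of choice. This stands, and it makes the point an optional improvement.

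A reader might go further and infer four things that the documents do not support.

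- *The covariate is certain to raise power, to at least about 92%.* The gain depends on correlations that are not printed. With 0.80/0.75/0.92 it is 0.1 point, and under pure decay it is nil. The top of the range needs readings a week apart to correlate no better than readings 12 weeks apart.
- *Visit 101 is an independent second measurement.* The two mornings are likely to be highly correlated, and that redundancy limits the gain.
- *Every randomised patient has the value.* That is so by design only. Protocol 9.4.1 sets readings near bronchodilator or systemic steroid use to missing. Patients with unacceptable eligibility spirometry (INCL05c in SAP 6.7) leave only the per-protocol set. As the table reads in the public copy, the medication-withholding question is not marked at Visit 101.
- *It costs nothing.* Protocol 9.4.2 would be changed, and protocol 11.1 governs amendments. Section 9 of the protocol plans pooling with an identical Phase 3 trial, which would need the same model.

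These points limit the claim without defeating it. The SAP already imputes missing baselines by the mean, and the statistical downside is negligible.

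**Conclusion.** The point holds as an efficiency gain open to the sponsor before unblinding. The planned analysis stays valid without it.

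The omission and the absence of bias follow directly from the documents. A smaller standard error is the expected direction, since only a second day can average out day-to-day variation. The size is uncertain: a variance factor of about 1.0 to 0.78, hence power of 90.3% to about 95-96%. At the top end this equals about 650/0.776 = 838 patients under the planned model.

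The gain would matter most where the sponsor's own assumptions slip. With a factor of 0.80, the stated 85.9% (20% discontinuation) becomes about 92% and the stated 80.9% (100 mL) about 89%. With a factor of 1.0 neither moves.

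The range rests on assumed correlations and on 380 mL being close to the residual SD. The variance factors also ignore any overlap between Visit 101 FEV1 and the other planned covariates.

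**What to change.** Before unblinding:

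1. In SAP 2.5.3.1, add Visit 101 pre-dose FEV1 as a further continuous covariate: the mean of the -45 and -15 minute readings, before bronchodilator, under the same censoring rules as Day 1, and imputed by the FAS mean if missing.
2. Add the same variable to the MMRM in SAP 2.5.5 and to the Covbytime list in SAP 6.6.1, so that the imputation and analysis models still match.
3. Keep the Day 1 mean as the baseline of the change score.
4. Record the departure from protocol 9.4.2 in SAP Section 4, or by amendment, and make the same change in the identical Phase 3 trial.
5. Take the Visit 101, Day 1 and Week 12 correlations from the Phase 2 study already used for the SD, and rerun SAP Table 3-1 to confirm the size of the gain.

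Cost: one degree of freedom in the ANCOVA, one coefficient per visit in the imputation model, and document and code updates. No new data and no patient burden.

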2.5.4 Handling of missing values/censoring/discontinuations

Retrieved data after the discontinuation of study drug (retrieved drop-out) will remain in the analysis without further imputation for all treatment groups.

Despite all attempts to ensure complete follow-up for all patients, some patients may not be followed for pre-dose FEV₁ for the whole planned study duration. Missing baseline pre-dose FEV₁ will be assumed to be missing at random (MAR) as assessments are performed prior to any knowledge of treatment allocation and will be imputed using the mean value of all randomized patients included in the FAS.

The FEV₁ value analyzed at each visit is based on the average of the two FEV₁ assessments taken at approximately 45 minutes and approximately 15 minutes prior to the dosing of study drug at clinic visits. In cases where one of the values is missing, this will be imputed within treatment group via multiple imputation and the average will be calculated based on the one available assessment and a second imputed assessment.

Once these imputations are complete, subsequent missing data will be imputed based on a jump-to-reference (J2R) approach according to following assumptions:

- Continued treatment effect will be imputed for QAW039 patients with intermittent missing data under a MAR assumption
- For QAW039 patients with missing data after discontinuation of double-blind treatment, imputation will be done based on placebo group under a J2R assumption
- Missing data in placebo group will be imputed under MAR assumption

The imputation and analysis will be implemented using the “five macros” available from www.missingdata.org.uk (for a full description see Carpenter et al (2013)). The first step in implementing this pattern mixture imputation approach is to fit a Bayesian Normal repeated measures model to estimate parameters from the observed on-study values (including on-treatment and off-treatment data). The model will include the same covariates as the primary model. Then use the estimated parameters to build possible predicted profiles for the unobserved values in a separate imputation model, one for each pattern of withdrawal. These profiles represent what we expect would happen to patients after they withdraw. Missing values for an individual are then imputed based on the profile of predicted means that matches their treatment, their time of withdrawal and other covariates. A large number of imputed datasets will be created, with their number chosen based on computational feasibility, but at least 1000. Observed and imputed data will be contrasted graphically. Each dataset will be analyzed using the model described in [Section 2.5.3.1](#) and the results will be combined using Rubin’s rule (Barnard and Rubin 1999) for final inference. A fuller description is given in the [Section 6.6.1](#) of the [Appendix](#).

Unless otherwise specified, for efficacy parameters, on-treatment data are defined as data on or after the first day of treatment with double-blind medication, but before or on the day of the last day of treatment with double-blind study medication; on-study data are defined as data on or after the first day of treatment with double-blind medication, but before or on the day of the last day of treatment period.

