6.6.1 Multiple imputations for primary and secondary variables

The imputation and analysis of primary and secondary variables will be implemented using the “five macros” available from www.missingdata.org.uk (for a full description see Carpenter et al (2013)). The purpose and activities of each of the five macros is described below.

Part1A declares the parameter estimation model and checks consistency with the input dataset. It builds a master dataset which holds details of the current job and also builds indexes for the classification variables, which may be either numeric or character.

Part1B fits the parameter estimation model using the MCMC procedure and draws a pseudo-independent sample from the joint posterior distribution for the linear predictor parameters and the covariance parameters.

Part2A calculates the predicted mean under MAR, and under MNAR for each subject based on their withdrawal pattern once for each draw of the linear predictor parameter estimates. The choice of MNAR is controlled by the method used, which may vary from subject to subject.

Part2B imputes the intermediate missing values using MAR and the trailing missing values using MNAR, by deriving the conditional distribution for the missing values conditional on the observed values and covariates, using the appropriate sampled covariance parameter estimates.

Part3 carries out a univariate ANOVA analysis at selected time points usually based on the same covariates as the parameter estimation model. It then combines the least-squares means and their differences using the MIANALYZE procedure to provide final results.

This is example code to implement the primary analysis:

```
%part1A(Jobname=fev1
,Data=RE
,Subject=subjid
,Response=aval
,Time=visit
,Treat=trt01pn
,Covbytime= basefev basescore basesaba
,Catcov=stratum
,
);
```

Where subjid = subject identifier

aval = change from baseline in FEV1 value at visit during the treatment epoch

visit = treatment period visit number

trt01pn = planned treatment

basefev = baseline FEV1 value

basescore = baseline daytime asthma symptom score

basesaba = baseline total daily SABA use

stratum = randomization strata (patient age (<18 years or \geq 18 years), use or not use a second asthma controller at study entry, region)

```
%part1B(Jobname=fev1
,Ndraws=1000
,thin=750
,seed=12345
);
%part2A(Jobname=fev1_J2R
,inname=fev1
,methodV=Mymethod
,refV=Myreference
);
```

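### Jump-to-reference switches to placebo after the last observed visit rather than at the stop of study drug, so QAW039 patients who give an off-drug reading and then leave are imputed, on average, below placebo

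*SAP*

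**What the plan says.** SAP 2.5.4 keeps retrieved off-drug readings in the analysis without imputation. It assigns J2R, with placebo as reference, to QAW039 values missing after double-blind treatment is discontinued, and missing at random (MAR) to intermittent gaps and to the placebo arm. The reason is in Table 2-2 of SAP 2.5.1: "Any fevipirant treatment effect would cease almost instantly after discontinuation of fevipirant, and only SoC effect is expected".

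The mechanics are as follows.
- The Bayesian repeated measures model is fitted to "estimate parameters from the observed on-study values (including on-treatment and off-treatment data" (SAP 2.5.4).
- The mean profile used for imputation is the one matching the patient's treatment, time of withdrawal and covariates (SAP 2.5.4).
- Part2B uses MAR for intermediate gaps and the not-at-random rule for trailing gaps only, "by deriving the conditional distribution for the missing values conditional on the observed values and covariates" (SAP 6.6.1).
- The example Part2A call passes one method variable and one reference variable. Nothing in it carries the date on which drug was stopped (SAP 6.6.1).

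Off-drug readings followed by withdrawal are foreseeable. Protocol 5.6.2 asks stoppers to attend a discontinuation visit and then to keep attending. Table 6-1 schedules spirometry and AQLQ+12 at the discontinuation visit. SAP 6.3 lets that visit stand in for a missed scheduled visit. SAP 2.6.4 applies the same imputation to the weekly diary means and to AQLQ+12.

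**The concern.** The rule is written in terms of stopping drug, but the implementation is written in terms of leaving the study. The two differ for a QAW039 patient who stops drug, gives at least one FEV1 reading off drug, and then misses Week 12. That reading sits at about placebo level if the effect ends at once. It is compared with a QAW039 profile well above placebo, so it looks like a poor result for that patient. The imputation then sets the later mean to placebo and adds the carried-forward share of that shortfall.

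At stake is agreement with the SAP's own rationale. These patients should centre on the placebo expectation, and as specified they centre below it. The primary difference is pulled towards zero and a little power is lost.

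**Working it through.** **Inputs from the documents.** SAP Section 3: "A difference of 112 mL in pre-dose FEV1 during treatment was assumed"; "The standard deviation (SD) of 380 mL and between-visit correlation for pre-dose FEV1 was based on study QAW039A2206"; "A treatment discontinuation rate of 15% was assumed based on QAW039A2206"; half of those who stop have Week 12 values; 325 per arm; testing "at the two-sided 5% significance level in the primary analysis". So 15% × 0.5 = 7.5% of the arm needs Week 12 imputation. Visits are at Weeks 2, 4, 8 and 12 (Protocol 3.1). The off-drug effect is zero at once (Table 2-2).

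**Assumptions.** The SAP does not state the between-visit correlation; 0.3 to 0.9 was used, exchangeable and AR(1). Stopping times are uniform, and each affected patient gives one off-drug reading. The share of non-retrieved stoppers who give one was varied.

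**Step 1: the plan's own power.** The standard error is 380 × √(2/325) = 29.8 mL. With every stopper at placebo level at Week 12, a two-sample power formula gives:

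| Effect, discontinuation | Diluted effect | Computed power | SAP Table 3-1 |
|---|---|---|---|
| 112 mL, 15% | 112 × 0.85 = 95.2 mL | 89.1% | 90.3% |
| 112 mL, 20% | 112 × 0.80 = 89.6 mL | 85.2% | 85.9% |
| 100 mL, 15% | 100 × 0.85 = 85.0 mL | 81.4% | 80.9% |

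An undiluted 112 mL gives 96.4%, and diluting by 7.5% only gives 93.5%; neither fits. The planning target is therefore about 95 mL, with stoppers at placebo on average.

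**Step 2: the formula.** Imputed Week 12 mean minus placebo mean = w′(y_obs − m_obs), where w holds the regression weights and m_obs is the profile up to the last observed visit. Under exchangeable correlation ρ, with k on-drug readings and then one off-drug reading, each weight is ρ/(1 + kρ). With the full 112 mL the shift is −112ρ/(1 + kρ):

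| ρ | k = 0 | k = 1 | k = 2 |
|---|---|---|---|
| 0.3 | −33.6 | −25.8 | −21.0 |
| 0.5 | −56.0 | −37.3 | −28.0 |
| 0.7 | −78.4 | −46.1 | −32.7 |
| 0.9 | −100.8 | −53.1 | −36.0 |

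**Step 3: the pooled mean.** The fitted arm mean includes off-drug data, so 112 mL is slightly too large. With ρ = 0.7 and half of the leavers giving an off-drug reading, the simulated pooled means are 109.9, 108.0 and 103.8 mL above placebo at Weeks 2, 4 and 8. Take a patient on drug at Week 2, off drug at Week 4, then gone. The residuals are 112 − 109.9 = +2.1 and 0 − 108.0 = −108.0, and the weight is 0.7/1.7 = 0.412. The shift is 0.412 × (−105.9) = −43.6 mL. With the switch at the stop date the second residual is 0 and the shift is 0.412 × 2.1 = +0.9 mL.

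**Step 4: the effect on the estimate.** With uniform stopping, a third of leavers stop after Week 8 and have no scheduled visit left before Week 12. At most 7.5% × 2/3 = 5.0% of the arm is then affected. In a large-sample simulation (200,000 per arm), the smallest shift in the estimate, a middle case and the largest were:

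| Structure, ρ, share of leavers | Arm affected | Imputed vs placebo | Estimate as specified | Switch at stop date | Difference | Power |
|---|---|---|---|---|---|---|
| AR(1), 0.3, 50% | 2.49% | −19.6 mL | 94.79 | 95.27 | −0.47 | 88.9% vs 89.2% |
| Exchangeable, 0.7, 100% | 5.09% | −44.2 mL | 92.61 | 94.90 | −2.28 | 87.4% vs 88.9% |
| AR(1), 0.9, 100% | 5.06% | −85.7 mL | 90.79 | 95.19 | −4.40 | 86.1% vs 89.1% |

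(Differences are from unrounded values.) Over all 16 scenarios affected patients centred 18 to 89 mL below placebo as specified, and within −2 to +3 mL of it with the switch at the stop date.

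A separate large-sample check, exchangeable with ρ 0.3-0.9 and 40-75% of non-retrieved stoppers giving one off-drug visit, put affected patients about 21-70 mL below placebo and the estimate 0.5-2.4 mL low. A multiple-imputation simulation at trial size (ρ 0.5-0.8, about three-quarters, no covariates) gave 92.1-93.0 against 94.9-95.2 mL, about 2 to 3 mL and within the wider range. The crude ceiling, with every non-retrieved stopper carrying the full effect, is 0.075 × 112 = 8.4 mL (power about 83%).

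**The case against.** The strongest reply is that the SAP states the right rule. SAP 2.5.4 ties J2R to treatment discontinuation, the listing in 6.6.1 is labelled an example, and the macros' internals lie outside the documents. It is true that the SAP never writes out the part of the profile before withdrawal, so the reading here rests on its description of the steps and the standard form of the method. But the rule in 2.5.4 says only which missing values get J2R. No sentence says which mean an earlier off-drug reading is measured against, and every operational statement points to withdrawal rather than to the stop date.

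Second, the residual may be smaller than assumed. The discontinuation visit is to be prompt, and Protocol 3.2 treats a week as covering at least five half-lives, so some drug effect may remain. After stopping, asthma therapy follows investigator judgement (Protocol 5.6.2). Remapping under SAP 6.3 is optional, and phone follow-up yields no spirometry. All of this stands, and it lowers the size without changing the direction.

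Third, other analyses look at missing data. The tipping-point analysis starts from these same imputations, and the on-treatment repeated measures model answers a different question. The retrieved-dropout imputation is moved outside the study report (SAP Section 4). None of these corrects the primary estimate.

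Fourth, using a patient's own off-drug readings to predict later visits is a reasonable choice. It is, and centring those readings on the placebo mean preserves it.

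**Conclusion.** The point holds as a mismatch between the stated assumption and the specified imputation, with a small and conservative effect. Affected patients centre about 20-90 mL below placebo. The primary estimate falls by about 0.5-2.4 mL if 40-75% of non-retrieved stoppers give one off-drug reading, and by up to about 4 mL in wider scenarios. Against a standard error of 29.8 mL that is 0.02 to 0.15 standard errors. Power falls by about 0.3-3 points. These figures rest on the assumed correlation, uniform stopping times, one off-drug reading per affected patient and immediate loss of effect.

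A reader might infer more than the documents support:
- That off-drug readings are compared with the pure on-drug mean. They are not; the fit pools on- and off-drug data, so the comparator is about 101-111 mL above placebo.
- That the loss of effect is counted twice in full. Only the share given by the regression weights is carried forward, and only on average, for stoppers who give an off-drug reading and then miss Week 12.
- That the trial's error rate is at risk. If the drug has no effect the arm means coincide and this bias disappears.
- That the planned 90.3% power is wrong. The SAP does not say how its simulations treated off-drug readings, and the reproduction in Step 1 is not sharp enough to tell.
- That the diary endpoints are biased by a known amount. They and AQLQ+12 use the same imputation, but the size was not calculated, and the documents do not say how often patients keep a diary off drug.

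**What to change.** State in SAP 2.5.4 and 6.6.1 that the J2R switch occurs at the date of double-blind treatment discontinuation, and say which mean applies to off-drug readings. Either of two implementations would do:

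- **(a) Mask and restore.** Set off-drug values to missing before Part1A, fit the model to on-treatment data, impute everything after the stop date by J2R (MAR for placebo), and put the observed off-drug values back before Part3. Retrieved data still enter the analysis as SAP 2.5.4 requires.
- **(b) Re-centre.** Keep off-drug readings in the conditioning set, but centre them on the placebo mean from the stop date onward.

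In the large-sample check both restored the target of roughly 95 mL. Apply the chosen rule also to the weekly diary means and AQLQ+12.

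The cost is SAP wording plus, for (a), a data step before and after the macros, or, for (b), a small change to the macro code. Under (a) a patient's off-drug readings no longer inform later imputed visits; (b) avoids that.
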